13.2. Analysis of Outcome Measures

13.2.1. Description of Analysis Methods

The analysis and presentation of the trial will be in accordance with CONSORT guidelines.[38] A full statistical analysis plan (SAP) will be developed and agreed prior to database lock and un-blinding of the analysing statistician.

Continuous variables will be summarised in terms of the mean, standard deviation, median, lower and upper quartiles, minimum, maximum and number of observations. Categorical variables will be summarised in terms of frequency counts and percentages. Descriptive statistics of demographic and clinical measures will be used to assess balance between the randomised arms at baseline, but no formal statistical comparisons will be made.

The primary approach to between-group comparative analyses will be by modified intention-to-treat (i.e. including all participants who have been randomised and without imputation of missing outcome data).

The primary comparative analysis will employ generalised linear regression modelling to compare the proportions in each group with a clinician-made diagnosis decision about the presence of an emotional disorder within 12 months of randomisation, adjusted for minimisation variables. The comparison will be presented as both an absolute (risk difference) and relative (risk ratio) effect, along with 95% confidence intervals.

Secondary outcomes will be analysed using appropriate regression models dependent on data type (binary, continuous, survival etc.), and will include factors used in the minimisation and baseline value of the outcome where measured. Where an outcome is also measured at multiple time points a mixed model will be fitted with a treatment by time interaction to obtain estimates of treatment effect at each follow-up time.

The analyses of secondary outcomes will be considered supportive to the primary and estimates and p-values, where presented, should be interpreted in this light.

Presentation of the diagnoses made and the subsequent treatment and interventions given will be descriptive. Frequency counts and percentages of the proportion of participants reporting each will be presented by treatment arms.

Safety outcomes will be presented descriptively according to allocation at randomisation, but no formal statistical comparisons will be made.

13.2.2. Sensitivity Analyses

We will repeat primary analyses additionally adjusting for any variables with marked imbalance at baseline to check that this does not influence the findings. We expect there to be <10% missing primary outcome data, but will plan sensitivity analyses using multiple imputation and/or simple methods making different assumptions to investigate the potential impact of missing data. We expect adherence with allocation to be high but will monitor throughout the study and, if appropriate, may consider an analysis to investigate the effects of adherence with the allocated intervention (level of participant completion of the DAWBA) using instrumental variable regression.

Trial name:	STADIA	Protocol version:	4.1	Date:	01-Aug-2022	Page:	60 of 73
Written using WPD 3							

13.2.3. Planned Sub Group Analyses

Appropriate interaction terms will be included in the primary regression analyses in order to conduct subgroup analyses according to the following subgroups:

- Sex of child (male or female)
- age (5-10 & 11-17 years)

Between-group treatment effects will be provided for each subgroup, but interpretation of any subgroup effects will be based on the treatment-subgroup interaction and 95% confidence interval, estimated by fitting an appropriate interaction term in the regression models. Since the trial is powered to detect overall differences between the groups rather than interactions of this kind, these subgroup analyses will be regarded as exploratory.

13.2.4. Planned Interim Analysis

There is no planned interim analysis of treatment efficacy. However, an assessment of recruitment and retention will be performed following the internal pilot phase to determine the feasibility or recruitment and acceptability of the intervention according to agreed progression criteria.

Decision to proceed or stop the trial

A Trial Steering Committee (TSC) meeting will be held shortly after the end of the Internal Pilot. The data on recruitment, retention and engagement will be presented, and the TSC will assess the predetermined acceptability and recruitment stop/go criteria and decide whether the trial can progress. Criteria will be set as follows for the number of participants randomised by the end of month 9 of recruitment (starting from first participant randomised):

- >90% of cumulative monthly randomisation target continue the trial.
- 60-90% of cumulative monthly randomisation target review recruitment/retention procedures to identify underlying problems and put in place strategies to address these, with review in 6 months by the TMG/TSC/DMC.
- 25-59% of cumulative monthly randomisation target review recruitment/retention procedures to identify underlying problems and put in place strategies to address these. Ongoing review over 6 months by the TMG/TSC/DMC and terminate the trial if the recruitment trajectory does not indicate that full recruitment can occur within an acceptable recruitment period.
- <25% of cumulative monthly randomisation target terminate the trial.

Retention at 6-month follow-up by the end of the pilot period will also be considered.

13.2.5. Planned Final Analyses

The final analysis will be performed when the recruitment and data collection are finished, data cleaning has been completed, the database is locked and the SAP agreed and signed off by relevant parties.

13.2.6. Power Calculations / sample size calculation

Assuming that 45% of participants randomised to the control arm will have a diagnosis of an emotional disorder within 12 months, 1088 participants (544 in each arm) are required to detect a 10% increase in diagnoses to 55% in the treatment arm, based on a two-sided test with 5% significance and 90% power.

Allowing for non-collection of the primary outcome in 10% of cases, a total of 1210 participants will be recruited (605 in each arm).

	Trial name:	STADIA	Protocol version:	4.1	Date:	01-Aug-2022	Page:	61 of 73		
1	Written using WPD 3.1 version 2.0 30-Oct-2017. Effective date: 30-Nov-2017. Template Author: [name]									

14. Health Economic Analysis

14.1. Aim

The primary economic analysis will take an NHS and personal social services cost perspective in accordance with NICE guidance, and a wider societal perspective to capture the broader effects. The secondary analysis will aim to establish potential broader effects on families and society by establishing time lost from work because of care of children with emotional difficulties and out-of-pocket expenses for the families. The combination of resource use and subsequent calculation of health service and societal cost will be combined with outcome and child/young person and parent/carer quality of life data to provide a measure of the cost effectiveness and cost utility of the use of the SDA tool versus usual care.

14.2. Health care resource use, including education and social care

A purposively designed resource use proforma will collect participant level resource information (see Table 7). This measure will collect data on all aspects of diagnosis, treatment and follow up including medication, inpatient and outpatient hospital visits and primary and community care use as well as societal and education costs. The measure includes sections specifically designed to quantify the effect on time off work for parents/carers (including friends and family) and the implications for productivity. In addition, it will seek to measure effects on time lost from education or training for the child/young person because of emotional difficulties. Ongoing development work will be undertaken during the pilot phase to improve clarity and enhance completion.

Table 7. Resource use data collection

Measurement	Data collection	Time point
A purposely designed resource use collection tool	Parent report	Baseline, 6 and 12
addressing primary, secondary, social care and patient	only for those	months post-
costs.	aged < 16.	randomisation
	Parent report (if	
	participating)	
	AND young	
	person self-	
	report for those	
	aged 16 & 17	

14.3. Outcome measures

The health economic analyses will utilise the following outcomes as defined in Table 8:

- Child/young person quality of life
- Parent/carer quality of life

Trial name:	STADIA	Protocol version:	4.1	Date:	01-Aug-2022	Page:	62 of 73		
Written using WPD 3.1 version 2.0 30-Oct-2017. Effective date: 30-Nov-2017. Template Author: [name]									

Outcome	Measurement	Definition	Data collection	Time point
Child/young person quality of life	Child Health Utility 9D (CHU9D)[39]	Quality- adjusted life years estimated using the CHU9D	Self-report by young person aged 11+ OR parent/carer report of child/young person aged <11 using CHU9D proxy OR parent/carer report of child/young person aged 11- 15 if not self- reported	Baseline, 6 and 12 months post- randomisation
Child/young person quality of life	EuroQol Quality of Life Questionnaire 5 Domains for Young People (EQ5DY)[40]	Quality- adjusted life years estimated using the EQ5DY	Self-report by young person aged 11+ OR parent/carer report of child/young person aged <11 using EQ5DY proxy OR parent/carer report of child/young person aged 11- 15 if not self- reported	Baseline, 6 and 12 months post- randomisation
Parent/carer quality of life	EuroQol Quality of Life Questionnaire 5 Domains, 5 Levels (EQ5D5L)[41]	Quality- adjusted life years estimated using the EQ5D5L	Self-report by the parent/carer	Baseline, 6 and 12 months post- randomisation

Table 8. Health economic outcome measurement

Health economic outcome data for children/young people will be collected using the EQ5DY and the CHU9D. Use of both measures will enable comparative analysis to be performed of the validity and acceptability of these two measures within the patient group. The two represent the most frequently used preference-based measures in children/young people. Eliciting comparative use of the two measures will provide a valuable resource for researchers going forward, who are seeking to incorporate an outcome-based preference measure into their research. Use of both measures will be evaluated during the pilot phase and if this is considered to impose too great a burden on respondents, the decision will be taken to continue with the collection of one measure only.

Trial name:	STADIA	Protocol version:	4.1	Date:	01-Aug-2022	Page:	63 of 73		
Written using WPD 3.1 version 2.0 30-Oct-2017. Effective date: 30-Nov-2017. Template Author: [name]									

14.4. Analysis

The net monetary benefit (NMB) framework will be used and a net benefit regression will be implemented; this allows multivariate analysis to explore baseline and centre-specific effects, which likely influence both clinical effect, cost, and their relationship. Resulting analysis would utilise generalized linear models (GLM), or if a highly skewed distribution of costs is observed a generalized Gamma model could be considered. The NMB framework estimates the extent to which, and the probability that, the SDA tool is cost effective compared to standard care at a range of threshold values (i.e. from £0 to £30,000) for the willingness to pay per QALY. Probabilistic sensitivity analysis (PSA) will be employed to calculate realised values; subsequently generating Cost Effectiveness Acceptability Curves (CEACs), which indicate the probability of being cost effective at the range of threshold values stated before.

Consideration can be given towards examining key cost drivers through sensitivity analysis.

15. Qualitative Study

15.1. Aim

The pilot will include a detailed qualitative component to address: a) the feasibility of recruitment; b) the acceptability and usability of the interventions and procedure; c) how the intervention is used and how this deployment could be refined (e.g. how the DAWBA is summarised and shared with participants and clinicians) for the main trial.

15.2. Methods

Semi-structured interviews will be conducted with up to 25 participants (parents and young people aged 16 and 17, from both the intervention and control arms of the study), 25 staff (including those recruiting participants, triage staff and clinicians) and 15 service managers and commissioners across the 5 sites. Principles of data saturation will be used to guide the final sample size. All interviews and analysis will be conducted by a qualitative researcher, with additional contributions from interested members of our Patient and Public Involvement (PPI) Advisory Group Panels in facilitating interviews and the analysis of emerging themes. The domains of the Consolidated Framework for Implementation will be used to develop the interview questions and as a coding framework for thematic analysis.[42].

Participants for the pilot phase qualitative study will be identified from the main trial, where they will have been asked to consent to being contacted by a qualitative researcher. Those who have consented will be contacted and asked if they want to participate, and if so will be sent a PIS and consent form (by email or post). Interviews will be arranged at a mutually convenient time and location. Where possible interviews will be conducted face-to-face, but where that is not feasible telephone or video call/skype interviews will be conducted. If telephone/video call interviews are conducted, verbal consent form will be recited by the researcher taking consent, and the participant asked to provide verbal responses. Verbal consent will be recorded as a separate audio file prior to the telephone/video call interview. If requested by the participant, the PIS may be delivered orally by the researcher prior to the telephone/video call interview.

Trial name:	STADIA	Protocol version:	4.1	Date:	01-Aug-2022	Page:	64 of 73	
Written using WPD 3.1 version 2.0 30-Oct-2017. Effective date: 30-Nov-2017. Template Author: [name]								

Staff, managers and commissioners at each site will be invited to take part in the interview study via the Principal Investigator at that site. The site PI will send potential participants the Letter of Invitation via email, which will request that those interested in taking part in the interview study make direct contact with the qualitative research team. Staff, managers and commissioners who volunteer to take part will be sent a PIS and consent form and the interview will be arranged for a mutually convenient time. Where possible interviews will be conducted face-to-face, but where that is not feasible telephone interviews will be conducted. Interviews will be arranged at a mutually convenient time and location. Group interviews with staff may also be conducted to facilitate the involvement of additional staff participants.

Interviews will be guided by the Interview Schedules and recorded using an encrypted digital recorder where consent is given. Digital audio files will be transferred to the transcription service Dict8 for transcription using secure FTP. Transcriptions will be anonymised. Audio files will be destroyed after transcripts have been checked. Anonymised transcriptions will be analysed and stored on password protected laptops and the secure University of Nottingham server.

15.3. Analysis

NVIVO 12 will be used to manage the qualitative data. All qualitative data will be analysed using interpretative and thematic approaches to coding, and adopt the framework method[43] which can support the involvement of the wider team, including PPI Advisory Group members, in qualitative analysis in multi-disciplinary health research projects. A qualitative analysis workshop will be held to allow the project team and interested PPI Advisory Group members to contribute to the discussion of emerging themes. The analysis will lead to a qualitative appraisal of the intervention and its implementation, and the production of recommendations about the future roll out and scale up in other settings.

15.4. Process evaluation

There will be a process evaluation alongside the main trial with the aim of identifying the barriers and facilitators to implementation. Using qualitative approaches, this study will produce evidence on how the intervention is introduced and operationalised in routine practice across the different sites, how it is experienced by different stakeholders, and what contextual factors and causal mechanisms affect outcomes, with the intention of producing learning for future implementation. The process evaluation will follow the MRC guidance and examine the quality of implementation, role of contextual factors, and mechanisms through which the outcomes occur.[44] A logic model for the process evaluation will be developed using the qualitative data from the internal pilot.[45] Semistructured interviews will be conducted with another 25 participants (parents and young people aged 16 and 17) and 25 clinicians taking part in the main trial to explore the perceived functioning of the intervention, the organisation of the service and reflective experiences on outcomes.

The methods and analysis will be the same as above, but different interview schedules will be used, which are to be developed following the results of the pilot phase qualitative work.

16. Trial Organisational Structure

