Qualitative study	Pilot Phase Interview Study Qualitative interviews will be conducted during the pilot phase to address: a) the feasibility of recruitment; b) the acceptability and usability of the interventions and procedure; c) how the intervention is used and how this deployment could be refined for the main trial. Semi-structured interviews will be conducted with up to 25 participants (parents and young people aged 16 and 17), 25 clinicians and 15 service managers and commissioners across the 5 sites.
	Main Trial Process Evaluation Study A process evaluation will aim to identify the barriers and facilitators to implementation of the intervention. Using qualitative approaches, this study will produce evidence on how the intervention is introduced and operationalised in routine practice across the different sites, how it is experienced by different stakeholders, and what contextual factors and causal mechanisms affect outcomes, with the intention of producing learning for future implementation. Semi-structured interviews will be conducted with another 25 participants (parents and young people) and 25 clinicians taking part in the main trial to explore the perceived functioning of the intervention, the organisation of the service and reflective experiences on outcomes.
	Analysis All qualitative interview data will be analysed using interpretative and thematic approaches to coding, and adopt the framework method. NVIVO 12 will be used to manage the qualitative data.

TRIAL FLOW DIAGRAM

* For sites where the waiting time for the CAMHS acceptance decision usually exceeds 10 working days from referral receipt, recruitment activities may start and/or continue beyond 10 working days from referral receipt, providing the intervention period can be completed prior to the CAMHS referral decision.

Trial name:	STADIA	Protocol version:	4.1	Date:	01-Aug-2022	Page:	11 of 73
Written using WPD	3.1 version 2.0 30)-Oct-2017. Effective d	late: 30-Nov-20)17. Templa	te Author: [name]		

CONTEN	ITS						
1. Bac	kground and Rat	ionale					17
1.1.	Background						17
2 Δim	s Objectives an	d Outcome Me	asures				18
2.1.	•						
	•						
2.2.	Outcome Measu	res		•••••			19
2.2.	1. Primary out	come					19
2.2.	2. Secondary o	utcomes					19
3. Tria	l Design and Set	ting					20
3.1.	0	0					
3.2.	Trial Setting						20
	-						
3.3.	Identification of	participants					20
4. Elig	ibility						21
4.1.	Inclusion criteria	for the child/yo	oung perso	n			21

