2.1. Aims and Objectives

The aim of the study is to evaluate the clinical and cost effectiveness of a Standardised Diagnostic Assessment (SDA) tool (the Development and Well-Being Assessment; DAWBA), as an adjunct to usual clinical care for children/young people presenting with emotional difficulties referred to Child and Adolescent Mental Health Services (CAMHS).

Specific objectives:

- 1. To conduct an RCT to determine the effectiveness of an SDA tool as an adjunct to usual clinical care on diagnosis and treatment of emotional disorders, symptoms of emotional difficulties and comorbid disorders and associated functional impairment.
- 2. To undertake an internal pilot phase of the RCT to assess recruitment and acceptability in all sites, with clear progression criteria to the full trial.

Trial name:	STADIA	Protocol version:	4.1	Date:	01-Aug-2022	Page:	18 of 73
Written using WPD	Vritten using WPD 3.1 version 2.0 30-Oct-2017. Effective date: 30-Nov-2017. Template Author: [name]						

- 3. To include a detailed qualitative component (see section 15) within the pilot phase to address: a) The feasibility of recruitment.
 - b) The acceptability and usability of the interventions and procedure.
 - c) How the intervention is used and could be refined for the main trial.
- 4. To conduct a process evaluation (see section 15.4) alongside the main trial which will:
 - a) Optimise the design and delivery of the DAWBA SDA tool in partnership with young people, parents and CAMHS professionals to enhance acceptability, effectiveness and long-term uptake.
 - b) Identify the barriers and facilitators to implementation of the DAWBA from the perspective of patients, parents, and CAMHS practitioners, managers and commissioners.
- To estimate cost effectiveness of the use of the DAWBA SDA tool versus usual care (see section 14).
- 6. To use the knowledge gained, from the perspective of all stakeholders, to make evidence-based recommendations for assessment procedures within CAMHS and produce practice guidelines for clinical decision-making around the referral acceptance and assessment processes.

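### Objective 4b assigns the manager and commissioner perspective to the main-trial process evaluation, but the sample in section 15.4 includes neither group

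*Protocol*

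**What the plan says.** Protocol section 2.1 separates two pieces of qualitative work. Objective 3 is the pilot component, covering feasibility of recruitment, acceptability and usability, and how the intervention is used and could be refined. Objective 4 is the process evaluation, introduced as "To conduct a process evaluation (see section 15.4) alongside the main trial which will" do two things. The second, 4b, is to "Identify the barriers and facilitators to implementation of the DAWBA from the perspective of patients, parents, and CAMHS practitioners, managers and commissioners". Objective 6 then promises recommendations and practice guidelines that reflect all stakeholders.

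Section 15.4 plans the process-evaluation interviews "with another 25 participants (parents and young people aged 16 and 17) and 25 clinicians taking part in the main trial". The Qualitative study row of the Trial Summary gives the same sample as "another 25 participants (parents and young people) and 25 clinicians taking part in the main trial".

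Managers and commissioners appear as interviewees only in the pilot. Section 15.2 lists, besides up to 25 families and young people, "25 staff (including those recruiting participants, triage staff and clinicians) and 15 service managers and commissioners across the 5 sites". Section 15.4 links the two phases: "A logic model for the process evaluation will be developed using the qualitative data from the internal pilot". It adds that methods and analysis carry over from the pilot, while the interview schedules will be new and will be written after the pilot results.

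**The concern.** The objective names five perspectives and points to one section for delivery. That section recruits from three of the five: patients, parents and practitioners. Managers and commissioners are left out of the interviews designed to examine how the tool was introduced and operated in routine practice, and what contextual factors and mechanisms shaped the results.

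At stake is how well the trial can answer its own implementation question for these two groups. Objective 6 builds practice recommendations on the views of all stakeholders. For managers and commissioners, those views would come only from pilot interviews, which answer to a different objective and use a different schedule.

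**Working it through.** No statistical calculation applies. The check compares the groups promised with the groups sampled, and counts the planned interviews.

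**Inputs**
- Groups promised: section 2.1, objective 4b.
- Process-evaluation sample: section 15.4 and the Trial Summary.
- Pilot sample: section 15.2.

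**Groups against samples**

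| Group in objective 4b | Pilot (15.2) | Process evaluation (15.4) |
|---|---|---|
| Patients and parents | up to 25 | 25 |
| Practitioners | 25 staff, including clinicians | 25 clinicians |
| Managers and commissioners | 15 | 0 |
| Total | up to 65 | 50 |

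**Counts**
- Process evaluation: 25 + 25 = 50 interviews, of which 0 are with managers or commissioners.
- Pilot: 25 + 25 + 15 = up to 65 interviewees, of which 15 are managers or commissioners.
- Both phases: 65 + 50 = up to 115, of which 15 are managers or commissioners (15/115 = 13%), all in the pilot.

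**Could the word clinicians in 15.4 include managers and commissioners?** No. Section 15.2 lists "15 service managers and commissioners across the 5 sites" as a category separate from staff and clinicians. The recruitment text in that section also names the three groups separately, and the Trial Summary makes the same distinction for the pilot.

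**Does the sentence carrying over the pilot methods bring the missing groups in?** Not on a natural reading. Section 15.4 states its own sample, repeats two of the pilot's three categories with fresh numbers, and omits the third. A general statement that methods carry over can supply the recruitment route and the analysis approach. It does not add a group that the sample leaves out.

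**Does the pilot put the same questions?** The protocol does not plan for that. The process-evaluation schedules are to be developed after the pilot results, so pilot respondents cannot have answered them unless they are interviewed again, and no re-interviews are described.

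**The case against.** The strongest reply is that the qualitative work is one linked programme and that managers and commissioners do have a voice in it. Several parts of the protocol support this:

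- The pilot questions and coding use the domains of an implementation framework (section 15.2), so barriers and facilitators are natural subject matter.
- The pilot also looks at how the intervention is used (section 15.1).
- Its analysis is to lead to an appraisal of implementation and to recommendations on wider roll-out (section 15.3), which is close to objectives 4b and 6.
- The pilot data feed the process evaluation's logic model (section 15.4).
- The objectives in the Trial Summary state the same aim for the study as a whole, without tying it to the process evaluation.

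All of this stands, and it limits the point. A reader might infer that the trial cannot deliver objective 4b. The documents do not support that: 15 managers and commissioners are interviewed on relevant subject matter, and the results are carried forward.

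A reader might also infer that the pilot comes too early for these respondents to have seen the tool in real use. The protocol does not say so. The pilot covers all sites, and progression is judged on randomisations to the end of month 9 of recruitment, so respondents may have had months of experience. If the pilot interviews finish by month 9 (an assumption), the first participant would be at least 12 − 9 = 3 months short of the 12-month primary outcome. That bears on what could be said about outcomes, not on whether implementation had been seen.

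Finally, section 15.4 limits young interviewees to ages 16 and 17, while the Summary refers only to young people. That could be read as a contradiction, but the Summary wording is better taken as a shortened form. Objective 4b sets no age for patients.

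What the reply does not remove is that section 2.1 assigns this perspective to section 15.4, and the sample there does not contain it.

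**Conclusion.** The mismatch is real and can be verified from the text. Objective 4b makes the main-trial process evaluation responsible for the manager and commissioner perspective, yet 0 of its 50 planned interviews are with those groups. Coverage is partial rather than absent, because 15 pilot interviews contribute. The specific gap is that these groups are not planned to be asked the process-evaluation questions about main-trial implementation.

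This rests on two readings: that the sample in section 15.4 is complete as listed, which the identical sample in the Summary supports, and that clinicians excludes managers and commissioners, which follows from how the protocol uses the terms elsewhere. The interview schedules are not in the protocol, so how far the pilot questions already cover 4b cannot be judged.

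The point is confined to the qualitative component and leaves the primary analysis, the sample size and the error rates untouched. It is worth making because the correction is cheap.

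**What to change.** Preferred: in section 15.4 and the Qualitative study row of the Trial Summary, allocate some of the 50 process-evaluation interviews to service managers and commissioners at the trial sites, using the process-evaluation schedule. The protocol gives no basis for a particular number; the saturation principle already stated in section 15.2 can guide it. Some of the pilot's 15 respondents could be interviewed again, and the pilot's invitation route through the site Principal Investigator can be reused.

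The cost is a wording amendment and slightly fewer family or clinician interviews, with the total unchanged at 50.

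Alternative: keep the sample and state in objectives 4b and 6 that manager and commissioner views come from the pilot interviews only. This removes the inconsistency at no cost in interviews, but leaves these groups' experience of main-trial implementation unexamined.
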